3.1 Primary Research Question

Does the administration of tamsulosin after the clinical and radiographic diagnosis of acute urolithiasis produces an increase in the proportion of patients passing their stone at 28 days by patient report?

3.2 Secondary Research Questions

The secondary research questions are whether tamsulosin produces a reduction in each of the following:

- Time to passage of stone
- Length of time in pain
- Number of days lost from work
- Need for surgical intervention or lithotripsy
- Overall costs
- Stone passage confirmation on CT scan
- Crossover to open label tamsulosin/Flomax

3.3 Design Summary

The multi-center trial will be conducted in the Departments of Emergency Medicine (ED) at The George Washington University Hospital in Washington D.C, Mercy Hospital of Pittsburgh and Presbyterian-University Hospital, both part of the University of Pittsburgh Medical Center, and Thomas Jefferson University Hospital. It is a continuation of the vanguard phase of the study performed solely at The George Washington University Hospital.

This research study is a blinded randomized controlled clinical trial of 400 patients in addition to the 109 enrolled in the vanguard phase. Patients diagnosed with kidney stones via radiographic imaging are approached for screening. Patients who satisfy the eligibility criteria and consent to randomization will be centrally randomized to one of the following two medical protocols, each to be taken once a day for 30 days:

◦ The active group who receive 30 tablets of 0.4 mg tamsulosin.◦ The placebo group who receive 30 similar inactive tablets.
--

3.4 Eligibility Criteria

3.4.1 Inclusion Criteria

1. Age \geq 18 years

2. Evidence of ureterolithiasis (i.e. stone is located in ureter) as demonstrated on CT with confident diagnosis. This does not include stones located in the bladder or solely in the kidney.
3. Willingness to participate and able to proceed with standard outpatient management (no personal or job-related issues, e.g. airline pilot).
4. Has a telephone in order to be contacted for follow-up.

3.4.2 Exclusion Criteria

1. Patient desiring or requiring immediate surgical intervention making them not a candidate for outpatient kidney stone management. (This includes prior surgery for the same stone).
2. Current urinary tract infection based on urine dipstick or micro urinanalysis as admission and urgent procedural management are likely indicated.
3. Known anatomical genitourinary abnormalities or prior GU surgeries. (Shockwave lithotripsy and ureteroscopy for prior stone(s) are not exclusionary.)
4. Positive pregnancy test making proper radiological imaging contraindicated.
5. Breastfeeding mothers.
6. History of hypersensitivity to tamsulosin.
7. Current use of alpha blockers or calcium channel blockers.
8. Current use of steroids which may have an independent effect on stone expulsion.
9. Spontaneous stone expulsion prior to enrollment.
10. Largest stone dimension \geq 9mm assessed using radiologic imaging, being very unlikely to pass spontaneously.
11. Previous treatment for the current ureteral stone not elsewhere classified (including shockwave lithotripsy, ureteroscopy and medications not currently being taken).
12. Current use of vardenafil which is tamsulosin contraindicated.
13. Ipsilateral, transplanted or solitary kidney as hospitalization may be necessary.
14. Known renal insufficiency (by patient history).
15. Fever defined as $>101.5^{\circ}\text{F}$ which may indicate infection.
16. Floppy iris syndrome which is tamsulosin contraindicated.
17. Planned cataract surgery in the next 60 days which is tamsulosin contraindicated.
18. Prisoners /wards of state.
19. Prior enrollment in STONE (Candidates who are screened and found ineligible may be rescreened at a later date.)

3.5 Randomization Method and Masking

Consenting patients will be assigned to one of the two treatment groups with a randomization sequence prepared and maintained centrally by the Biostatistical Coordinating Center (BCC). The active and placebo study medication will be packaged according to the randomization sequence, so that the patient is randomized when he or she is assigned to the next available individual supply of study medication. The study is double masked; neither the patient nor the clinical staff will be aware of the treatment assignment.

The simple urn method will be used to generate the randomization sequences because it provides a high probability of balance in treatment assignments, it is unpredictable, and it allows an explicit randomization analysis,^{48,49} to be conducted with relative ease. Randomization will be stratified by clinical site to assure balance between the two treatment groups with respect to anticipated differences within the clinic populations and possible differences in patient management.

4 Study Procedures

4.1 Screening and Randomization

Potential study subjects will be identified while present in the Emergency Department. While the patient is in the ED, a member of the research team will be notified. This researcher will determine if the patient meets the inclusion and exclusion criteria. If the patient meets enrollment criteria, the study protocol will be explained to the patient. If they express interest in participation, informed consent will be obtained, randomization will take place, study medications will be dispensed, and urological follow-up will be arranged before the patient is discharged from the ED.

4.2 Medical Treatment Protocol

The placebo group will receive placebo plus active analgesia, and the active treatment groups will receive analgesia together with a thirty day course of tamsulosin. Standard follow-up care will be offered. Other than administration of tamsulosin or placebo, there will be no differences in the approach to treatment. Any treating physicians will be blinded to treatment group. A one-page guideline for enrolled patients to bring to their physician to help further standardize treatment has been designed.

4.3 Study Outcomes and Ascertainment

4.3.1 Primary Outcome

The administration of tamsulosin after the clinical and radiographic diagnosis of acute urolithiasis produces an increase in the proportion of patients passing their stone within 28 days.

Determination of the symptomatic stone

In cases in which there is more than one stone noted on the CT scan, the physician treating the patient will determine the likely location and dimensions of the stone causing symptoms by reviewing the patient's ED record.

Multiple stones

If the physician believes that the symptomatic stone has not yet reached the bladder the patient may be offered enrollment. If there are multiple stones and the physician believes that the stone causing symptoms has reached the bladder, the patient will not be eligible for enrollment.

Definition of stone expulsion

Stone expulsion will be defined as a report by the patient that the stone was noted to have passed by visualization or capture after urination and that the pain has been relieved.

4.3.2 Secondary Outcomes

The secondary outcomes are:

- Length of time in pain
- Surgical intervention or lithotripsy
- Cost savings based on days of work lost, surgical interventions, hospitalizations, etc.
- Time until stone expulsion
- Total amounts of analgesia taken
- Days of work lost

- Complications including repeat ED visits or other hospitalizations
- Stone passage confirmation on CT scan
- Crossover to open-label tamsulosin/Flomax

Together with these secondary hypotheses, a secondary objective is to identify the most appropriate clinical subgroup(s) for treatment.

4.4 Baseline Procedures

In this randomized clinical trial, the following data and procedures will be performed at screening:

- Informed consent
- Eligibility
- Medical history
- Physical exam
- Labs: dipstick urinalysis
- Labs: pregnancy test for females
- Labs: hematology and/or serum chemistry, *if clinically indicated*
- Result of CT scan

4.5 Patient Management and Follow-up

After randomization, patients are contacted on days 2 and 7, and then on days 15, 20, 29 (to capture status through Day 28), and finally on day 90, as outlined below along with the procedures to be completed in this study and frequency that they will be performed. All the interventions and clinical follow-up in this study are those normally performed in the treatment of patients diagnosed with nephrolithiasis. The only treatment that is not routine is taking tamsulosin or placebo. Follow-up data will be collected in one of three ways: telephone follow-up is the most preferred method, but email communication or texting to the patient's cell-phone can also be used in the case that a telephone call is not feasible.

Table 3: Phone call follow-up Days 2-90

	Day 2	Day 7	Day 15	Day 20	Day 29	Day 90
Study drug taken	X	X	X	X	X	
Total NSAIDs taken	X	X	X	X	X	-
Total Percocet taken	X	X	X	X	X	-
Other analgesics taken?	X	X	X	X	X	-
Stone captured?	X	X	X	X	X	X
Returned to work?	X	X	X	X	X	X
Side effects: Dizzy/nausea/other	X	X	X	X	X	-
Seen PCP for follow-up?	X	X	X	X	X	X
Seen urologist for follow-up?**	X	X	X	X	X	X
Any return ED visits?	X	X	X	X	X	X
Hospitalizations?	X	X	X	X	X	X
Surgical interventions for the stone?	X	X	X	X	X	X
Stone seen on any repeat CT/KUB?	-	-	X	X	X	-
CT scan	-	-	-	-	X	-

**if the patient was seen for urology follow-up, data regarding repeat urinalysis and blood pressure will be collected.

4.5.1 CT scan at 29 days

A follow-up low dose CT scan of the abdomen and pelvis will be performed at day 29 (with a window to day 36). If a documented CT was done outside the study before 29 days that shows passage, it will be

reviewed by the PI who will determine if the information is comparable and sufficient. If so, the study CT will not be performed. This scan will be used in conjunction with the follow-up data to confirm stone passage.

4.6 Adverse Event Reporting

Detailed information concerning adverse events will be collected and evaluated throughout the conduct of the protocol. Results of clinical observations, laboratory tests, and reported events form the basis for evaluating the safety profile of this therapy. At all contacts, patients will be questioned regarding side effects or symptoms associated with the study medication which are as follows:

- Dizziness at rest
- Dizziness on standing (postural hypotension)
- Abnormal ejaculation (in men)
- Gastrointestinal disorder
- Peptic ulcer disease
- Gastrointestinal bleeding
- Urinary tract infections
- Facial flushing
- Headache
- Tachycardia
- Other side effects

The clinical center will report adverse events to the coordinating center in a timely fashion. The coordinating center will summarize and report adverse events to the DSMB.

Additional procedures are warranted for cases of serious adverse events which is defined by the FDA as a patient outcome that is: (1) death; (2) life-threatening, i.e., the patient was at substantial risk of dying at the time of the adverse event or it is suspected that the use or continued use of the product would result in the patient's death; (3) hospitalization (initial or prolonged); (4) disability, i.e., resulted in a significant, persistent, or permanent change, impairment, damage or disruption in the patient's body function/structure, physical activities or quality of life; (5) congenital anomaly, i.e., there are suspicions that exposure to a medical product prior to conception or during pregnancy resulted in an adverse outcome in the child; (6) requires intervention to prevent permanent impairment or damage. Serious adverse events will be reported immediately to the NIDDK project office, the BCC and the local IRB. The BCC will notify the DSMB chair; and the entire DSMB will confer if needed.

The only indication for breaking the randomization code is when it is medically necessary to unmask the study drug assignment to be able to treat the patient, such as an allergic reaction or severe side effect that appears to be related to the medication.

5 Statistical Considerations

Our data analysis is designed to evaluate the following goals of the study: 1) to determine the efficacy of tamsulosin with respect to primary and secondary outcomes in patients with urolithiasis, 2) to ensure that such treatment is safe 3) to determine if benefit is equally evident across a range of clinically relevant subgroups. The principal analyses of primary and secondary outcomes employ the intent-to-treat (ITT) approach. Although data may be missing at points in time, all relevant data available from each participant will be employed in all analyses. An ITT analysis more closely reflects actual conditions and experiences of clinical practice than analyses based on the subset of 'complete' or 'totally compliant' participation and, therefore, does not overestimate the impact of an intervention. Treatment group assignments are not altered based on adherence to the assigned treatment regimen. Furthermore, applying ITT maintains the benefits of randomization; if dropouts and non-compliers are ignored, then the study design becomes more observational and bias due to post-randomization subset selection is introduced. All significance tests will be 2-sided, with alpha=0.05.

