A recent study reported safety experience with 1784 patients receiving 0.4 mg tamsulosin for six months (with a total drug exposure time of 811 patient years).²² The most frequent adverse events are shown below in Table 1. Intraoperative floppy iris syndrome has been reported frequently in patients on tamsulosin undergoing cataract surgery. Complications from this syndrome can be minimized as long as the ophthalmologist is aware that the patient is taking tamsulosin.²³ In logistic regression analysis alpha-blockers, converting enzyme inhibitors, diabetic medications and diuretics did not significantly affect the odds ratio for having an adverse event. However, concomitant alpha-antagonists (a protocol violation) and treatment with verapamil (which also has alpha-antagonist activity) significantly enhanced the odds ratio for having an adverse event to 3.87 (CI 1.52-9.85) and 3.17 (CI 1.52-6.58), respectively. Minor increases in the odds ratio, which did not reach statistical significance, were also observed for Ca^{2+} antagonists other than verapamil and for nitrates. In a study of 756 patients with benign prostatic hypertrophy randomized to tamsulosin (0.4 and 0.8mg/day) or placebo, the incidence of positive orthostatic test results in the tamsulosin groups was comparable to that observed in the placebo group.²⁴

While there are differences in the incidence of various side effects among alfuzosin, doxazosin, tamsulosin and terazosin, the overall side-effect profiles of these agents have been characterized as “very similar” by the Alpha-Blocker Committee at the 4th International Consultation on BPH.²⁵ The results of seventeen trials examining the safety and efficacy of various alpha-blockers were reviewed by Lowe, who concluded that therapy with these agents is “...well tolerated, and the majority of side effects with alpha-blockers are mild to moderate, seldom causing patients to prematurely discontinue therapy”.²⁶ The blood pressure effects of tamsulosin are comparable to those of either terazosin²⁷ or doxazosin,²⁸ although tamsulosin was associated with a lower level of nocturnal orthostatic hypotension.²⁷

Table 1 Most frequent adverse events during a 6 months treatment with 0.4 mg tamsulosin o.d.²²

Adverse Event	N	%	(95% CI)
Dizziness	45	2.5	(1.85, 3.36)
Abnormal ejaculation	29	1.6	(1.09, 2.33)
Headache	29	1.6	(1.09, 2.33)
Hypotension	26	1.5	(0.95, 2.13)
Gastrointestinal disorder	18	1.0	(0.60, 1.59)
Nausea	17	1.0	(0.56, 1.52)

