5.3.2 Testing of efficacy and safety outcomes

One of the secondary endpoints is whether the patient requires a more complicated treatment within 90 days of the index emergency visit. This would be evidenced by the need for surgical intervention or lithotripsy. Based on the practice characteristics of the research site we expect a low number of these cases. In addition, work by Yilmaz³⁶ described above lends strong evidence to our expectation that the

surgical intervention rate will be low. These cases will be described descriptively. The two study groups will be compared using the Pearson chi-square test or the Mantel-Haenszel procedure if covariate adjustment is necessary. An additional secondary outcome is the number of days of work missed. These will be tested by t-test or (or ANCOVA with covariates), or if necessary because of distributions requirements, by the Wilcoxon test.

To examine whether the treatment groups experience comparable rates of complications we will monitor patients for several unlikely but potential complications of tamsulosin as outlined above. Events not typically associated with patients with acute urolithiasis will be classified as adverse effects. Adverse and serious adverse events are expected to occur at a very low rate in both study conditions. These will be analyzed descriptively.

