5.4 Sample Size and Power

5.4.1 Sample size

The primary outcome for the STONE study is the proportion of patients who pass stones within 28 days. Data on stone passage rates is summarized in a meta-analysis by Hollingsworth et al³⁷ who found the baseline occurrence of stone passage in the control group across nine studies to be 47% with rates ranging from 20% to 73%. The lower confidence limit of the passage rate in the treatment group across the nine studies was 68%. A two group chi-squared test with a 0.05 two-sided significance level will have 90% power to detect the difference between a placebo proportion of 0.45 and a tamsulosin proportion of 0.60 when the sample size in each group is 250 accounting for losses to follow-up.

Due to concerns that the passage rate might be inappropriate, this sample size will be achieved in a two-stage approach. After the outcomes of the treatment of the first 100 patients were obtained, the passage rate in the placebo group was calculated by the BCC. The DSMB reviewed the data and agreed that the total sample size of 500 was accurate. Therefore, the remainder of the sample will be collected in a multi-center trial. There will be approximately 200 more patients randomized to each treatment group along with the 109 patients randomized in the pilot study, would achieve the total sample size of 500 patients.

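### Safety is a stated analysis goal, but adverse events get only descriptive analysis with no between-arm estimate or interval, and 250 per arm leaves about 2 to 3 points of uncertainty

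*Combined protocol and SAP*

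**What the plan says.** Section 5 (Statistical Considerations) opens with three goals for the data analysis. The second is "2) to ensure that such treatment is safe".

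Section 5.3.2 introduces its safety paragraph with "To examine whether the treatment groups experience comparable rates of complications". The complications meant there are the potential harms of tamsulosin. The paragraph continues "Adverse and serious adverse events are expected to occur at a very low rate in both study conditions" and ends "These will be analyzed descriptively". It names no risk difference, risk ratio, confidence interval, test or margin.

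The word complications has a second use. Section 4.3.2 lists repeat emergency department visits and other hospitalizations as a secondary outcome under that name. Section 5.5 sends dichotomous secondary outcomes to the primary-outcome methods: Pearson chi-square, or logistic regression if adjustment is needed.

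The sample size in Section 5.4.1 rests on efficacy alone: "A two group chi-squared test with a 0.05 two-sided significance level will have 90% power" for "a placebo proportion of 0.45 and a tamsulosin proportion of 0.60", "when the sample size in each group is 250 accounting for losses to follow-up". No precision or power figure is given for safety.

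**The concern.** An analysis goal should be matched by an analysis that can address it. *Ensure* is an unqualified word, and whether two rates are comparable is a between-arm question. A side-by-side table of counts shows each arm but not how large a difference the data leave open.

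With few events per arm, similar percentages are easily read as evidence of no difference. If the report then says that tamsulosin was safe, or that complications were comparable, the reader cannot tell from the planned tables what excess risk was actually ruled out.

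**Working it through.** **Inputs**
- 250 per arm, 1:1 (Section 5.4.1 and Appendix A).
- Event rates: Table 1 in Section 2.1.1 gives dizziness 2.5% and hypotension 1.5%. These are six-month, tamsulosin-only figures, whereas this trial gives 30 days of drug. The documents give no 30-day or placebo rates, so I assume equal true rates of 1.5% to 2.5% in both arms.
- Margins of 2, 3 and 5 points are my assumption, because the documents state none.

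**1. The plan's own figure.** For 0.45 against 0.60, two-sided 0.05 and 90% power, with mean proportion 0.525:

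n = [1.960·√(2·0.525·0.475) + 1.282·√(0.45·0.55 + 0.60·0.40)]² / 0.15² = 231 evaluable per arm.

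250 per arm therefore implies losses of 1 − 231/250 = 7.6%. With a continuity correction n is 244, implying 2.4%. The 250 is consistent with the efficacy inputs.

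**2. Precision of a risk difference.** Half-width = 1.96·√(2p(1−p)/250).
- p = 2.5%: 1.96·√(0.04875/250) = 2.74 points.
- p = 1.5%: 1.96·√(0.02955/250) = 2.13 points.

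Newcombe score intervals for equal counts are slightly wider: ±3.0 points for 6 v 6 events and ±2.6 for 4 v 4. A doubling would be an excess of 2.5 or 1.5 points, which lies inside the interval in each case.

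**3. Relative scale.** Risk ratio interval for equal counts x = exp(±1.96·√(2/x − 2/250)).
- 6 v 6: 0.33 to 3.06.
- 4 v 4: 0.25 to 3.95.

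**4. Power to detect a doubling (Pearson chi-square, 250 per arm).** 31% for 2.5% to 5%; 20% for 1.5% to 3%. For 80% power, 906 and 1,534 per arm would be needed.

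**5. What can be excluded.** The chance that the upper 95% limit falls below a margin m, given equal true rates, is Φ(m/√(2p(1−p)/250) − 1.96).

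| Margin | p = 1.5% | p = 2.5% |
|---|---|---|
| 2 points | 45% | 30% |
| 3 points | 79% | 57% |
| 5 points | over 99% | 95% |

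A 5-point excess over 2.5% is a tripling, to 7.5%.

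**6. Zero events.** One-sided 95% upper bound for 0/250 = 1 − 0.05^(1/250) = 1.19%.

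**7. Sensitivity to losses.** With 231 evaluable per arm, the half-widths become 2.8 and 2.2 points and the zero-event bound 1.3%.

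**The case against.** The strongest reply is that descriptive safety tables are a common choice in a trial sized for efficacy, and that the plan nowhere says how it would declare tamsulosin safe. Several parts of that reply stand.

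- A reader might infer that Section 5.3.2 promises to demonstrate comparable rates. It does not: it sets out to examine whether they are comparable. Only *ensure* in Section 5 is a strong claim.
- A reader might infer that no complication is formally compared. Repeat emergency department visits and hospitalizations are, through Sections 4.3.2 and 5.5. That route does not clearly reach the side effects listed in Section 4.6, such as dizziness on standing, and a chi-square p-value alone gives no interval.
- A reader might infer that 250 per arm can support no safety conclusion. That depends on a margin the documents do not give, and step 5 shows that a 5-point excess can be excluded.
- Describing data does not forbid confidence intervals. The plan simply does not name them.
- Patients are questioned about side effects at every contact, serious events are reported immediately, and the monitoring board reviews adverse events and may recommend stopping for harm (Sections 4.6, 5.2 and 6.4). This protects patients during the trial, but it does not define what the final report may conclude.

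The rates are also borrowed. Lower 30-day rates would narrow the absolute intervals and widen the relative ones.

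**Conclusion.** The concern holds in a limited form. Section 5 sets a safety goal that the named method does not address, because adverse and serious adverse events are to be described with no between-arm estimate or interval specified.

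On the assumption of equal true rates of 1.5% to 2.5%, 250 per arm leaves about ±2 to 3 points of uncertainty on each risk difference. An excess of 5 points can be excluded with about 95% probability or more. A doubling of risk cannot be excluded when the observed rates are equal. No events in an arm would still be compatible with a true rate of 1.2%.

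The documents do not support the wider reading that the trial is unable to say anything about safety, or that the plan claims to prove equivalence. Intervals would show the imprecision but not remove it, so the goal itself also needs rewording. The point is a worthwhile improvement in wording and reporting and leaves the primary analysis untouched.

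**What to change.** - **Section 5, goal 2:** restate as estimating the difference in adverse events between tamsulosin and placebo.
- **Section 5.3.2:** replace the descriptive-only sentence with counts, percentages and the risk difference with a 95% score interval (Newcombe or Miettinen-Nurminen). Do this for each of the 11 items in Section 4.6, for any adverse event and for any serious adverse event. Use men only as the denominator for abnormal ejaculation.
- **Label:** state that these intervals are for estimation and are not adjusted for multiplicity.
- **Conclusion rule:** limit any safety statement to the excess risk that the upper confidence limit excludes. For example, 6 v 2 events in 250 per arm would be reported as +1.6 points (Newcombe 95% interval −0.8 to +4.4), so an excess above 4.4 points is excluded and smaller ones are not.

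**Cost:** no extra patients or data; a few sentences and one more table column. About 13 unadjusted intervals will be shown (11 + 2), so an isolated one may exclude zero by chance. The safety claim becomes slightly less favourable.
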